## 1 ADMINISTRATIVE STRUCTURE AND VERSION HISTORY

This study is being conducted under the sponsorship of Exelixis, Inc. Exelixis is responsible for statistical design and planning. Statistical programming and analyses are being conducted under contract by Array Inc. in conjunction with Exelixis, Inc.

This version of the Statistical Analysis Plan (SAP) is based on the original protocol dated April 30, 2018.

**Table 1: Protocol Version History**

| Date          | Version           | Primary Reason(s) for Amendment |
|---------------|-------------------|---------------------------------|
| 30 April 2018 | Original Protocol | Not Applicable                  |

**Table 2: SAP Version History**

| Date              | Version  | Primary Reason(s) for Amendment |
|-------------------|----------|---------------------------------|
| 09 September 2020 | Original | Not Applicable                  |

## 2 STUDY DESCRIPTION

### 2.1 Study Design

This is a Phase 3 multicenter, randomized, double-blinded, placebo-controlled trial of cabozantinib in subjects with radioiodine (RAI) refractory differentiated thyroid cancer (DTC). Best supportive care (BSC) will be provided for subjects on both treatment arms. The multiple primary efficacy endpoints for the study are progression-free survival (PFS) and objective response rate (ORR) assessed per blinded independent radiology committee (BIRC). Approximately 300 subjects will be randomized in a 2:1 ratio to receive either cabozantinib or placebo.

Each subject's course of treatment will consist of the following periods:

**Pre-treatment Period:** Potential subjects will be screened to determine if they meet the required eligibility criteria. Qualifying screening assessments must be performed within 28 days before randomization unless otherwise specified.

**Treatment Period:** Subjects who meet all study eligibility criteria will be randomly assigned in a 2:1 ratio to receive blinded study treatment cabozantinib or placebo. Subjects on both treatment arms will be treated with BSC. This excludes non-protocol anticancer therapy (NPACT).

**Crossover Phase:** As subjects in the study population have limited treatment options, and to minimize the potential for differential dropout among subjects randomized to placebo with respect to the PFS endpoint as assessed by BIRC, the study will allow eligible subjects randomized to placebo to crossover to receive cabozantinib upon experiencing radiographic disease progression (PD) per RECIST 1.1 that is confirmed by the BIRC. To facilitate this:

- A real-time dual-reader adjudicated BIRC review of radiographic images per RECIST 1.1 will be employed to document objective radiographic progression contemporaneously with subject study participation.
- At the time of investigator-determined radiographic progression per RECIST 1.1, investigators may request from the Sponsor's medical monitor (or designee) confirmation of BIRC-determined radiographic PD.
- For subjects with BIRC-confirmed radiographic progression:
  - Upon authorization from Sponsor's medical monitor (or designee), investigators may unblind individual subjects via the Interactive Response Technology (IRT) system.
  - Unblinded subjects randomized to placebo have the following options:
    - Such subjects may be provided by the Investigator the opportunity, if eligible (see Protocol Appendix B), to enter the Crossover Phase to receive cabozantinib and undergo study assessments per Protocol Appendix B.
    - Such subjects who are ineligible or opt not to crossover to receive cabozantinib are to have study treatment discontinued and proceed with post-treatment assessments as described in Protocol Appendix A.
    - Unblinded subjects randomized to cabozantinib may continue on study treatment if the investigator believes the subject is still deriving clinical benefit. Study assessments are to continue per Protocol Appendix A.
- Subjects without radiographic progression per BIRC will not be unblinded and are to continue to receive blinded study treatment and undergo study assessments according to the schedule in Protocol Appendix A. Safety assessments will continue, efficacy

assessments will be per standard of care if allowed per local regulation; PK, biomarker, and health-related quality of life (HRQOL) will be discontinued.

Further, the entire study may be unblinded if the PFS endpoint results are sufficiently compelling, with similar options for subjects to cross-over (or continue) to receive cabozantinib after unblinding.

**End of Study Treatment:** Subjects will receive blinded study treatment or unblinded treatment with cabozantinib as long as they continue to experience clinical benefit in the opinion of the investigator or until there is unacceptable toxicity or the need for non-protocol systemic anticancer treatment. Treatment may continue after radiographic PD per RECIST 1.1 as determined by the investigator in the absence of non-protocol systemic anticancer treatment as long as the investigator believes that the subject is still receiving clinical benefit from study treatment and that the potential benefit of continuing study treatment outweighs potential risk.

**Post-Treatment Period:** A post-treatment follow-up visit will occur 30 (+14) days after the date of the decision to discontinue study treatment. See protocol ‘Study Design’ Section 3 for details.

**Maintenance Phase:** After the primary efficacy endpoints of ORR and PFS have been analyzed and declared to be successful and upon determination by the Sponsor that sufficient data have been collected to adequately evaluate all study endpoints to establish, for regulatory purposes, the safety and efficacy profile of the experimental drug within this study, the study will begin to transition to the Maintenance Phase.

As a transitional step prior to initiation of the Maintenance Phase, all blinded study subjects will be unblinded and study sites will be notified of their randomized treatment assignments. Subjects on the placebo arm, if eligible will have the opportunity to cross over to receive cabozantinib treatment. See protocol ‘Study Design’ Section 3 for details.

## **2.2 Study Treatment**

Eligible subjects will be randomized in a 2:1 ratio to the following treatment arms:

- Cabozantinib arm: Oral cabozantinib (60 mg) daily (qd)
- Placebo arm: Oral cabozantinib-matched placebo qd

In addition, all subjects will also receive BSC.

### **2.3 Study Objectives and Endpoints**

The primary objective of this study is to evaluate the effect of cabozantinib compared with placebo on PFS and ORR in subjects with RAI-refractory DTC who have progressed after prior VEGFR-targeted therapy.

This study has two primary efficacy endpoints. The trial will be declared a success if the null hypothesis is rejected for either of these endpoints; rejection of the null hypotheses for both endpoints is not required. The protocol refers to these as “co-primary” endpoints, but per recent conventions these are “multiple primary” endpoints (FDA Guidance for Industry: Multiple Endpoints in Clinical Trials [draft, January 2017]). This plan employs this FDA convention.

#### **2.3.1 Primary Efficacy Endpoints**

The primary efficacy endpoints are:

- Progression-free survival (PFS) per Response Evaluation Criteria in Solid Tumors (RECIST 1.1) by BIRC (see Section 8.1.2.4)
- Objective response rate (ORR) per RECIST 1.1 by BIRC (see Section 8.1.1.1)

#### **2.3.2 Additional Endpoints**

- Overall survival (OS)
- Duration of objective tumor response
- Safety and tolerability (see Section 9)
- Pharmacokinetics (PK) (see Section 8.4.8)
- Relationship of baseline and post-baseline changes in serum thyroglobulin (Tg), will be performed (see Section 8.4.5)
- Change in mobility, self-care, usual activities, pain/discomfort, anxiety/depression, and global health as assessed by the EuroQol Health questionnaire instrument (EQ-5D-5L) (see Section 8.4.6)
- Health care resource utilization (see Section 8.4.7)

## 2.4 Power and Sample Size Justification

The study is designed to provide adequate power for both co-primary endpoints of ORR and PFS. It is estimated that 100 subjects would be adequate to evaluate the co-primary endpoint of ORR alone, and 300 subjects will be needed to evaluate the co-primary endpoint of PFS. Thus, to allow an earlier evaluation of ORR, this study employs a “trial within a trial design” (Hessel et al 2016). The primary analysis of ORR will be limited to the first 100 subjects randomized to the study and defined as the OITT population. Analysis of ORR is expected to occur 6 months after the last subject is enrolled in this population.

For ORR, 100 subjects provide a 2-sided 0.01 test of difference in proportions with > 90% power to reject the null hypothesis of no difference in ORR, assuming a true ORR of 2% in the placebo arm and 35% in the cabozantinib arm (a 33 percentage point difference), a pooled variance estimate, and a 2:1 allocation ratio.

For the primary endpoint of PFS, assuming exponential distribution, proportional hazards, and a 2:1 treatment allocation ratio (cabozantinib:placebo), 193 events are required to provide 90% power to detect an HR of 0.61 using the log-rank test and a 2-sided significance level of 0.04. This corresponds to a 36% reduction in the risk of progression or death, or a 64% improvement in median PFS from 5.5 months to 9.0 months. Under this design and with the application of the fallback method (see Section 8.2) the minimum observed effects that would result in statistical significance for PFS are:

- If Ho is rejected for ORR and PFS is tested at the 5% level under the fallback method, the minimum observed effect that would result in statistical significance for PFS is:

| Analysis | Information Fraction | p-value | HR    | Median PFS (months) |              |
|----------|----------------------|---------|-------|---------------------|--------------|
|          |                      |         |       | Placebo             | Cabozantinib |
| Interim  | 43%                  | 0.0013  | 0.474 | 5.5                 | 11.6         |
| Final    | 100%                 | 0.0496  | 0.742 | 5.5                 | 7.4          |

- If Ho is not rejected for ORR and PFS is tested at the original 4% allocation, the minimum observed effect that would result in statistical significance for PFS is:

| Analysis | Information Fraction | p-value | HR    | Median PFS (months) |              |
|----------|----------------------|---------|-------|---------------------|--------------|
|          |                      |         |       | Placebo             | Cabozantinib |
| Interim  | 43%                  | 0.0008  | 0.469 | 5.5                 | 11.7         |
| Final    | 100%                 | 0.0397  | 0.738 | 5.5                 | 7.5          |

With a constant accrual rate of 20 subjects per month and using a 2:1 treatment allocation ratio, a total of 300 subjects (200 in the cabozantinib arm, 100 in the placebo arm) are required to observe the required number of PFS events within the planned study duration (15 months accrual; approximately 20 months to observe the required events).

Power and sample size estimates were calculated using EAST v5 by Cytel Software.

## 2.5 Randomization and Blinding

This is a randomized, double-blind, placebo-controlled study of cabozantinib in subjects with RAI-refractory DTC after prior VEGFR-TKI therapy. Cabozantinib-matched placebo will be given in the placebo arm to blind (mask) study treatment.

Until individual subjects or the study has been unblinded (see Section 2.1), study treatment assignment will be unknown to the subjects, investigators, study centers, Sponsor, and any Contract Research Organization (CRO) affiliated with the study other than those authorized to access treatment assignment for regulatory safety reporting and submission processes (see Protocol Section 8.2.2), IRT system administration, and drug supply management.

Sponsor personnel will remain blinded until the earlier of successful rejection of the null hypothesis for the ORR or the time of primary PFS analysis. Should the analysis of ORR reject the null hypothesis, limited sponsor personnel will be unblinded for the purposes of data analysis and submission to Regulatory agencies. Unblinded full-study data will not be

released to or shared with the operational study teams at Exelixis, the CRO, investigators, or study subjects until after the analysis of the PFS endpoint.

When an individual subject has been deemed eligible at the study site, the site representative will use the designated interactive response technology (IRT) to enroll the subject into the study. Eligible subjects will be randomly assigned in a 2:1 ratio to receive either cabozantinib or placebo.

Randomization will be by permuted blocks stratified by the following factors:

- Receipt of prior Lenvatinib (yes or no)
- Age at informed consent ( $\leq 65$  years vs.  $> 65$  years)

### **3 ANALYSIS POPULATIONS**

#### **3.1 Intent to Treat Population**

The Intent-To-Treat (ITT) population is defined as all randomized subjects regardless of whether any study treatment or the correct study treatment was received.

#### **3.2 Overall Response Rate Intent to Treat Population**

The Overall response rate Intent-To-Treat (OITT) population is defined as the first 100 randomized subjects regardless of whether any study treatment or the correct study treatment was received.

#### **3.3 Safety Population**

The Safety population will include all randomized subjects who receive any amount of study treatment (either cabozantinib or cabozantinib-matched placebo). Analyses based on the Safety population will be performed according to the actual treatment received. Subjects who receive both treatments in error will be summarized in the cabozantinib group.

#### **3.4 Overall Response Rate Safety Population**

The Overall response rate Safety (O-Safety) population will include the subjects included in the OITT population receiving any amount of study treatment (either cabozantinib or cabozantinib-matched placebo).

### **3.5 Per Protocol Population**

A Per Protocol population is not defined or planned for the study.

## **4 GENERAL CONVENTIONS**

The statistical principles applied in the design and planned analyses of this study are consistent with International Conference on Harmonization (ICH) E9 guidelines (ICH 1998).

Continuous data will be summarized using descriptive statistics (number of observations, mean, standard deviation, median, 25th and 75th percentiles, minimum, and maximum). Frequencies and percentages will be used for summarizing categorical (discrete) data.

Confidence intervals, when presented, will generally be constructed at the 95% level. For binomial variables, the Clopper-Pearson's method will be employed unless otherwise specified.

A month is operationally defined to be 30.4375 days. Six months is operationally defined to be 183 days.

All summaries will be presented by treatment arm unless otherwise specified.

### **4.1 Analyses, Reports, Treatment Periods and Summary Groups**

Up to four analyses milestones are planned over the course of the study, with treatment periods shown below:

1. Primary ORR + interim PFS [Blinded treatment period]
2. Final PFS [Blinded treatment period except for subjects who were individually unblinded for potential crossover]
3. Safety update for 120-day report [Blinded treatment period]
4. Final safety update, upon initiation of the Maintenance Phase [Blinded and Open-label treatment periods]

Up to four study reports are planned:

1. Primary clinical study report (CSR), written the first time the null is rejected for either of the primary efficacy endpoints, or if all primary testing is completed without rejection of either null.

2. CSR efficacy addendum, written if analyses #2 is successful subsequent to success of ORR in analysis #1
3. 120-Day safety update written to include results from analysis #3
4. Final CSR safety addendum, written to include analysis #4

Details on the interim analysis of PFS and the control of type 1 error are provided in [Sections 8.3](#) and [8.2](#).

Data collected for this study can be grouped by the following two treatment periods in which it was obtained:

**Blinded Period:** In this phase of the study subjects receive either cabozantinib or placebo and the treatment identity is unknown to them.

**Open-label Period:** At the time of investigator-determined radiographic progression per RECIST 1.1 that is confirmed by BIRC subjects may be individually unblinded. Further, the entire study may be unblinded if the PFS endpoint results are sufficiently compelling. At such time, subjects will have the following options:

- Subjects randomized to the placebo arm may discontinue study treatment (if still on treatment) or, if eligible, cross over to receive cabozantinib after unblinding
- Subjects randomized to the cabozantinib arm still receiving study treatment may discontinue study treatment or continue to receive cabozantinib

For both treatment arms the date of registration for treatment with unblinded cabozantinib recorded in the IRT will define the start of the Open-Label Period.

Efficacy summaries (other than OS) will be based on data obtained in the Blinded Period for the two treatment arms – cabozantinib and placebo.

**Table 3: Schema for Efficacy Summaries**

|                             |  |  |
|-----------------------------|--|--|
| Treatment Period:    | Blinded Period   |  |
| Group:               | Subjects randomized to cabozantinib (Cabozantinib arm) | Subjects randomized to placebo (Placebo arm) |
| Start Date of Period | Randomization Date                                     |  |

Safety summaries (adverse events, exposure, etc.) will be categorized in the following groups:

- (a) Subjects randomized to and treated with cabozantinib (Cabozantinib arm),
- (b) Subjects randomized to placebo but receiving cabozantinib after crossover (Placebo crossover arm),
- (c) Subjects who received cabozantinib at any time, i.e., subjects randomized to and receiving cabozantinib, and the subjects randomized to placebo and receiving cabozantinib after crossover, and
- (d) Subjects randomized to and receiving placebo until crossover or end of treatment

Table 4: Schema for Safety Summaries

| Treatment:            | Cabozantinib  |  |   | Placebo  |
|------------------------------|--|--|---|---|
| Group:                | Subjects randomized to and receiving cabozantinib (Cabozantinib arm)  | Subjects randomized to placebo but receiving cabozantinib after crossover (Placebo crossover arm)   | All subjects receiving cabozantinib including crossover subjects (All Cabozantinib arm)  | Subjects randomized to and receiving placebo (Placebo arm)   |
| Start Date of Period: | Date of 1 st dose of cabozantinib   | Date of 1 st dose of cabozantinib after crossover   | Date of 1 st dose of cabozantinib  | Date of 1 st dose of placebo   |
| End Date Of Period:   | Earlier of the date of last date of exposure to cabozantinib+30 days, or date of withdrawal of consent by subject, or date of death, or date of data cut-off | Earlier of the last date of exposure to open-label cabozantinib +30 days, or date of withdrawal of consent by subject, or date of death, or date of data cut-off | Earlier of the last date of exposure to cabozantinib +30 days, or date of withdrawal of consent by subject, or date of death, or date of data cut-off | Earlier of the last date of exposure to placebo, or date of withdrawal of consent by subject, date of death, or date of receipt of open-label cabozantinib -1, or date of data cut-off. |

#### 4.2 Definition of Baseline

In general, for efficacy endpoints the last observed measurement prior to randomization will be considered the baseline measurement. Exception to this rule are efficacy biomarkers such

as pharmacogenetics blood samples, biomarker samples, bone marker samples and blood samples for potential circulating tumor cell (CTC) analyses. These samples per schedule of assessment were collected after randomization but prior to the Dose Day 1 (see definition Table 4 above), hence the baseline measurements will be with respect to this date. For subjects who did not take any study treatment, any biomarker sample available prior to randomization will be considered as baseline observation.

For safety endpoints the last observation before Dose Day 1 will be considered the baseline measurement unless otherwise specified. For assessments on Dose Day 1 where time is not captured, a nominal pre-dose indicator, if available, will serve as sufficient evidence that the assessment occurred prior to Dose Day 1.

Assessments on Dose Day 1 where neither time nor a nominal pre-dose indicator are captured will be considered prior to Dose Day 1 if such procedures are required by the protocol to be conducted before first dose.

For placebo subjects who crossover to receive cabozantinib, the second baseline will be defined as the last date of observation prior to the first date of open-label cabozantinib.

### **4.3 Definition of Study Day**

For efficacy data summaries for: (a) ORR/PFS in the blinded phase and (b) OS, Study Day is defined with respect to the randomization date. For visits (or events) that occur on or after randomization, study day is defined as (date of visit [event] – date of randomization + 1). For visits (or events) that occur prior to randomization, study day is defined as (date of visit [event] – date of randomization). There is no Study Day 0. To explore efficacy endpoints such as ORR or PFS for placebo subjects who cross over to receive cabozantinib in the open-label phase Study Day will be calculated with respect to date of registration for cross over in the IRT.

For the various safety data summaries, Dose Day 1 is defined in Table 4 of Section **Error! Reference source not found.** above. Dose day for visits (or events) that occur on or after Dose Day 1, is defined as (date of visit [event] – Dose Day 1 + 1). Dose day for visits (or events) that occur prior to Dose Day 1, is defined as (date of visit [event] – Dose Day 1). There is no Dose Day 0.

For listings (such as for adverse events [AEs]) that include the derivation of “days since last dose,” this is defined as (event date – date of last dose). Events that occur on the same day as

the last dose of study drug will therefore be described as occurring zero days from the last dose of study drug.

#### **4.4 Visit Window Calculation**

Analyses will be according to actual visit dates and times. The planned analyses do not require the calculation of visit windows. However, for analyses that require a particular visit as planned, measurements included in that visit must have occurred during the acceptable window defined for the visit in the protocol, unless otherwise specified in this plan.

#### **4.5 Missing and Partial Data**

In general, other than for partial dates, missing data will not be imputed and will be treated as missing. The algorithms for imputation of partial dates vary depending upon the parameter. These are presented in Appendix A.

#### **4.6 Safety Observation Period**

The safety observation period is defined as follows for the summaries described above in Section 4.1:

The safety observation period for subjects randomized to and receiving any cabozantinib is defined as the time between the date of first dose of cabozantinib to the earlier of the date of last dose of cabozantinib +30 days, or date of withdrawal of consent by subject, or date of death, or date of data cut-off.

The safety observation period for all subjects receiving placebo only during the blinded treatment period is defined as the time between the date of first dose of placebo to the earlier of the date of last dose of placebo, or date of withdrawal of consent by subject, date of death, or date of receipt of open-label cabozantinib -1, or date of data cut-off.

Subjects crossing over from placebo to cabozantinib will have data from the crossover period summarized independently. The post-crossover safety observation period of all subjects receiving cabozantinib after crossing over from placebo is defined as the time between the date of first dose of open-label cabozantinib to the earlier of the date of last dose of open-label study treatment +30 days, or date of withdrawal of consent by subject, or date of death, or date of data cut-off.

Generally only the safety data (including adverse events, laboratory results, vital signs, ECG, ECOG PS, concomitant medications and etc.) reported during the safety observation period will be analyzed and summarized, unless otherwise specified in this plan.

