## 8 SAFETY

### 8.1 Adverse Events and Laboratory Abnormalities

An AE is any untoward medical occurrence in a patient or clinical investigation subject who has been enrolled in a clinical study and who may have been administered an investigational product, regardless of whether or not the event is assessed as related to the study treatment. An AE can therefore be any unfavorable and unintended sign (including an abnormal laboratory finding), symptom, or disease temporally associated with the use of an investigational product, regardless of whether or not the event is assessed as related to the investigational product. This definition also includes events associated with medication errors and uses of the investigational product outside of what is in the protocol, including misuse and abuse. Preexisting medical conditions that worsen during a study should be recorded as AEs. Abnormal laboratory values, ECG findings, or vital signs are to be recorded as AEs if they meet the criteria described in Section 8.3.

All untoward events that occur after informed consent through 30 days after the date of the decision to discontinue study treatment are to be recorded by the investigational site. At each scheduled and unscheduled visit, AEs are to be identified and assessed based upon study procedures, routine and symptom-directed clinical investigations, and subject query/report.

Assessment of the relationship of the AE to the study treatment by the investigator will be based on the following two definitions:

- **Not Related**: An event is assessed as not related to study treatment if it is attributable to another cause and/or if there is no evidence to support a causal relationship.
- **Related**: An event is assessed as related to study treatment when there is a reasonable possibility that the study treatment caused the event. Reasonable possibility means there is evidence to suggest a causal relationship between the drug and the event. This event is called a suspected adverse reaction. A suspected adverse reaction implies a lesser degree of certainty about causality than adverse reaction, which means any AE caused by a drug.

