### **9.6.1 Adverse Events**

Adverse event terms recorded on the CRFs will be mapped to preferred terms using the Medical Dictionary for Regulatory Activities (MedDRA) dictionary. The investigator will classify the severity of AEs using the CTCAE v5 and will judge each event to be “not related” or “related” to study treatment.

A treatment emergent adverse event (TEAE) is defined as any event that begins or worsens on or after date of first dose of study treatment.

The frequency and percentage of subjects with TEAEs will be tabulated for overall incidence by system organ class and preferred term by treatment arm. Related TEAEs, serious TEAEs, related serious TEAEs, TEAEs resulting in study treatment discontinuation and TEAEs resulting in study treatment modification (either dose reduction or dose delay) will be similarly summarized. TEAEs and related TEAEs will also be summarized for worst reported severity within each subject.

At each level of summarization, a subject will be counted only once for each AE preferred term he/she experiences within that level (ie, multiple episodes of events with the same preferred terms will be counted only once).

All reported subject deaths will be summarized by treatment arm, cause of death, and relationship to study treatment.

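### The SAP's safety window runs to last dose + 30 days on cabozantinib but stops at the last dose on placebo, which biases placebo adverse event incidence downward

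*Combined protocol and SAP*

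**What the plan says.** SAP 4.6 ends the period for subjects randomized to cabozantinib at the "earlier of the date of last dose of cabozantinib +30 days", withdrawal of consent, death or data cut-off. The post-crossover period has the same 30 days. The placebo period is "the time between the date of first dose of placebo to the earlier of the date of last dose of placebo", withdrawal of consent, death, "or date of receipt of open-label cabozantinib -1, or date of data cut-off".

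Table 4 in SAP 4.1 repeats the difference. Its cabozantinib columns add 30 days; its placebo column reads "Earlier of the last date of exposure to placebo, or date of withdrawal of consent by subject, date of death", followed by the crossover and cut-off limits. Safety group (d) in 4.1 fits this: "Subjects randomized to and receiving placebo until crossover or end of treatment".

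According to 4.6, generally only safety data from this period "will be analyzed and summarized, unless otherwise specified in this plan". SAP 9.1 tabulates only treatment-emergent AEs (TEAEs) with onset inside the window. SAP 9.2 sets no other window for events to monitor. Laboratory, vital sign, ECOG and ECG summaries (9.5 to 9.8) use the same one.

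The protocol makes no distinction by arm. Under protocol 8.1, events "through 30 days after the date of the decision to discontinue study treatment are to be recorded". Protocol 9.6.1 defines a TEAE as "any event that begins or worsens on or after date of first dose of study treatment", with no end date for either arm.

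**The concern.** Events in the 30 days after the last dose enter the incidence tables for one arm only. TEAEs count whatever their cause, so those days will contain background and disease-related events in both arms. Placebo is the reference for the TEAE and events-to-monitor tables, for the odds ratio, relative risk and risk difference table, and for the table of terms with an increase of at least 5% (all grades) or 2% (Grade 3/4). A reference that is too low inflates each of these contrasts.

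Two related problems follow. The AE rates in SAP 9.3 divide by treatment exposure as defined in 6.5, which ends at the decision to discontinue and adds no 30 days. If the numerator follows 4.6 and 9.1, post-dose cabozantinib events are counted with no matching person-time. The overall summary in 9.1 also contains Grade 5 rows defined as up to 30 days after the last dose, a period that the placebo window excludes.

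**Working it through.** The documents state no TEAE incidence for this trial, so there is no planned figure to reproduce. The direction follows from the definitions; the size needs assumptions.

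**Is there a stated or implied reason?** Crossover does not supply one, because the cap on the day before open-label cabozantinib already prevents overlap. Data availability does not either: provided the decision does not precede the last dose, last dose + 30 days is never later than decision + 30 days, so the events are collected. SAP 4.9 does not list the rule as a change.

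**Direction.** The placebo window lies inside the window it would have under the cabozantinib rule. Placebo incidence as planned can therefore only be lower or equal.

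**Inputs for size.**
- From the documents: accrual 20 per month over 15 months; final PFS analysis at about month 20; first analysis at 100/20 + 6 = month 11; median PFS 5.5 (placebo) and 9 months (cabozantinib).
- Assumed: the same constant AE hazard h in both arms, 0.01 to 0.10 per month; time on treatment T exponential with median PFS as a proxy; last dose equal to the decision date.
- L = 30/30.4375 = 0.986 months. F is follow-up to cut-off, with uniform entry.

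**Formulas.** Exposure = min(T, F). Window with 30 days = min(T + L, F). Incidence = mean of 1 − exp(−h × window), by simulation with 1.5 to 3 million subjects per arm. In the crossover case, a random half of placebo subjects have the window min(T + 7 days, F).

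**Check by hand, placebo at month 20.** λ = ln 2/5.5 = 0.126, and F is uniform on 5 to 20. The share off treatment is 1 − (e^(−5λ) − e^(−20λ))/(15λ) = 1 − (0.5325 − 0.0804)/1.890 = 0.761. Mean exposure is 0.761/λ = 6.04 months. The 30-day window averages 6.77 months, so about 0.73 months (10.8%) is lost.

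**Placebo understatement, percentage points.**

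| h per month | Month 20, no crossover | Month 20, half cross over within 7 days | Month 11, no crossover | Month 11, half cross over |
|---|---|---|---|---|
| 0.01 | 0.7 | 0.4 | 0.4 | 0.3 |
| 0.03 | 1.9 | 1.2 | 1.1 | 0.7 |
| 0.05 | 2.9 | 1.8 | 1.8 | 1.1 |
| 0.10 | 4.7 | 2.9 | 3.1 | 1.9 |

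Using instead the median treatment durations of the two placebo-controlled trials in protocol 1.3, the month 20 range without crossover is 0.65 to 4.25 (6.5/10.6 months, sorafenib trial) and 0.8 to 5.6 (3.9/13.8 months, lenvatinib trial).

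**Grade 3/4.** Protocol 1.3 cites per-term placebo rates of 0 to 2.4%. Solving h so that planned placebo incidence at month 20 is 1.0, 1.4 or 2.4% gives an understatement of 0.12, 0.17 or 0.29 points under the planning medians (0.08, 0.11 or 0.18 with crossover).

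**Share of the apparent gap with no true difference.** At month 20 and h = 0.05, placebo is 24.3% as planned and 27.2% with 30 days; cabozantinib is 32.2%. The gap is about 8.0 points as planned and 5.1 with equal windows. The window accounts for roughly 36%, and longer cabozantinib exposure for the rest.

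**SAP 9.3.** With equal hazards, and no post-dose days on placebo, the rate ratio is mean cabozantinib window/mean cabozantinib exposure = 8.32/7.75 = 1.07 at month 20 and 4.52/4.23 = 1.07 at month 11. Equal windows with the 6.5 denominator unchanged give 0.96. Matching numerator and denominator days within each arm gives 1.00.

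The 1.07 depends on the last dose being the decision date. Suppose all subjects are off treatment, with exposures of 9 months (273.9 days) and 5.5 months (167.4 days), and with c and p days held before the decision on cabozantinib and placebo. The ratio is [(273.9 − c + 30)/273.9] / [(167.4 − p)/167.4].

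| c (days) | p (days) | Ratio |
|---|---|---|
| 0 | 0 | 1.11 |
| 14 | 0 | 1.06 |
| 28 | 0 | 1.01 |
| 14 | 14 | 1.15 |
| 0 | 14 | 1.21 |
| 0 | 28 | 1.33 |

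**Grade 5 rows.** The lead-in to the 9.1 overall summary limits every row to the safety observation period, except rows marked as counting at any time. The 30-day Grade 5 rows carry no such mark, so on placebo the two rules collide. The 9.4 deaths table defines its own periods, which 4.6 permits.

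**The case against.** The strongest defence is that the rule is deliberate and harmless. Section 4.6, Table 4 and group (d) agree with one another, and an on-treatment definition for placebo is a coherent choice. The protocol sets a collection period and a TEAE onset rule and leaves analysis details to the SAP, so a reader who infers a breach of the protocol goes too far. The internal consistency stands, but it supplies no reason for counting post-dose background events in one arm only.

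A reader might also infer that the rule hides a cabozantinib risk. It does the opposite: a lower placebo reference makes cabozantinib look worse and flags more terms. Nor does it account for the whole gap that would appear without a true difference. At month 20 most of that is longer exposure, which equal windows do not remove.

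The larger figures have no anchor in the documents. Neither document gives per-term all-grade placebo rates, and the hazards, the 50% crossover and the 7-day gap are assumed. Several events to monitor, such as perforation, fistula and posterior leukoencephalopathy, are described as less frequent, so the effect there is likely near the bottom of the range. Post-dose placebo events still appear in the AE listings. All of this lowers the priority; none of it removes the bias.

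For 9.3, the section does not restate its numerator window, so the mismatch is read from 4.6 and 9.1. It would also be wrong to say that 9.3 can be repaired only together with the placebo window, since matching its denominator to its numerator is enough.

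**Conclusion.** The point holds as a bias in descriptive safety tables, of low to moderate priority. Confidence is high for the asymmetry and its direction, and much lower for the size. About 0.7 to 4.7 points at month 20 (0.4 to 2.9 if half of placebo subjects cross over within 7 days) rests on equal constant hazards and planning-median exposure. The 9.3 null ratio of about 1.07 rests in addition on the last dose being the decision date, and it moves with dose holds. The Grade 5 conflict is a matter of wording and needs no assumption. SAP 9 plans no formal safety comparison, and no efficacy conclusion is touched.

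**What to change.** 1. In SAP 4.6 and Table 4, end the placebo window at the earliest of last placebo dose + 30 days, the day before the first open-label cabozantinib dose, withdrawal of consent, death or data cut-off. Use one term in both places; 4.6 now refers to the last dose and Table 4 to the last date of exposure.
2. Separately, in 9.3 use the same interval for numerator and denominator in each arm. Either take the safety observation window for both, or count only onsets during 6.5 exposure over that exposure. The second keeps the table adjusted for treatment duration, as its title says.
3. In the 9.1 overall summary, extend the exemption to the Grade 5 rows limited to 30 days after the last dose, in both arms.

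The cost is SAP wording and minor reprogramming of the 9.1 to 9.3 tables and the other summaries that use the window, with no new data. SAP 9.9 already foresees an amendment that could carry the change. Placebo AE rates will rise slightly, early crossovers will still contribute fewer than 30 post-dose days, and the difference due to longer cabozantinib exposure will remain in the crude incidence tables.
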